#### Assessments(120 minutes)

- fMRI assesses neural target engagement and treatment outcomes. fMRI is a standard technique for measuring and mapping brain activity that is noninvasive and safe. In this study, it is being used simply to gather neuro imaging data, and not to test the safety/efficacy of a device or software. Afterwards, the patient completes blood pressure, height, and weight measurements. (90 minutes)
- Self-report surveys of PST theory-based constructs of emotion (affect, worry) and cognition (problem solving, dysfunctional attitudes) as well as patient outcomes (e.g., depressive and anxiety symptoms, functioning, quality of life). Participants may complete these surveys during or outside their fMRI visits. (30 minutes).

### Self-completed Ecological Daily Assessments (<3 minutes each day)

Using the Lumen companion application participants complete ecological end-of-day assessments of mood, stress, appraisal, and coping for 7 days every 2 weeks (over 16 weeks).

**Intervention Orientation.** Participants in the intervention arm attend a Lumen orientation visit (60 minutes) during which they will be given a Lumen intervention tutorial and receive a study iPad, configured to limit access to only the Lumen intervention enabled on the device. Before leaving participants are scheduled for the first PST session with Coach Lumen. As needed, Lumen intervention orientations can be done remotely.

**Intervention data collection.** Secure study iPads used by participants in the intervention arm are enabled with Lumen PST. Participants complete 8 PST sessions beginning with 4 weekly and then 4 biweekly intervals over 12 weeks on their assigned iPad. At the end of each PST session, participants are prompted to schedule their next session with Coach Lumen. They receive automated reminder notifications 1 day prior to their next session and on the session day and have the opportunity to make up missed sessions. Intervention participants also complete the PHQ9 and GAD7 and user experience surveys at all PST sessions. Upon completion of the intervention participants will receive a certificate of completion signed by [name]. They may also complete a post-intervention interview via Zoom to characterize participant perspectives regarding their Lumen use experience.

**Intervention fidelity assurance.** All PST sessions that participants complete with Lumen are audiorecorded. Session recordings and transcripts are stored on the Amazon Web Services (AWS) in study configured accounts, with coded identifiers (see Section 7.). These materials will be used to evaluate treatment fidelity and user-Lumen interaction.

## **7.0 Expected Risks/Benefits**

This is a minimal risk study with prudent measures in place to protect the health and well-being of research participants and their privacy and confidentiality. Risks associated with participation in this study may include the potential for the following:

- Potential for self-harm
- MRI-related injury, discomfort, and distress (Aim 2: pilot RCT only)
- Patient privacy and confidentiality breach
- Accidental recording.

These risks are largely associated with the characteristics of the patient population to be studied and the procedures involved in the research. The target population includes patients with moderate, untreated depressive and/or anxiety symptoms. The risks are reasonable in relation to the anticipated benefits and are minimized by using procedures that are consistent with sound research designs and established research and clinical protocols. The following measures are implemented to minimize potential risks to participants in the study.

**Protection against risks of self-harm.** Some of the questions about depression, thoughts of death and other psychological symptoms and conditions as a part of study assessments may cause discomfort for some participants. However, in general the questions are not particularly intrusive or distressing, and stress is likely transient. In addition, participants are free to refuse to answer any questions. It is widely accepted that asking questions about thoughts of death or suicide does not lead to increased risk of suicide. Nevertheless, in the event that a patient is identified as being suicidal during the screening or follow-up phase of the study, the following self-harm protection protocol (adapted from the UIC IRB

approved ENGAGE-2 study #2018-1174), is in place to immediately alert the study supervising psychiatrist to assess the patient’s suicidal thoughts by telephone, followed by notification of the participant’s PCP and appropriate clinical action if necessary. If a participant responds “1” (“several days”), “2” (“more than half the days”), or “3” (“nearly every day”) to the PHQ-9 question “Over the last 2 weeks, how often have you been bothered by thoughts that you would be better off dead or thoughts of hurting yourself in some way?”, we further assess the participant’s level of risk by asking “Do you have a plan for how you would commit suicide?” and then follow the protocol based on the assessed level of risk. Individuals reporting suicidal ideation on PHQ9 with an active plan at eligibility screening are excluded from participation. Nonetheless, the risk of emergent suicidality still exists after enrollment. Risk for suicide may be detected when a participant completes the PHQ9 at the beginning of each PST session with Lumen. Participants who score 1-3 (see above) on item 9 of the PHQ9, will be offered the option to call an emergency contact, the national [name]/[name] hotline, or 911 at the time of detection. This information is a pre-programmed script for Lumen. The supervising study psychiatrist, [name], the intervention manager, [name], receive immediate notifications, as outlined in the table below. The study psychiatrist calls the participant within 3-4 days to conduct an assessment, assess need for further referral, and discuss referral options depending on urgency, needs and preferences, available supports in place, insurance status and routine source of care. The study psychiatrist may refer the participant for immediate comprehensive evaluation (e.g., at a local emergency department), ambulatory psychiatric services, or community resources, with personal accompaniment depending on the evaluation outcome.

[If PHQ9 completed with SPEAC study staff by phone]	

If YES, participant has active plan for self-harm:
 
 
• Explain to participant: I am concerned for your safety and therefore need to call for help right now.
 
• Get participant's location
 
• Stay on the phone with participant and use another phone to call 911.
 
 
[Script: "I want to report a self-harm alert for a UI Health research participant who has just endorsed suicidal ideation to me (by phone) - I want to provide his/her name, location, and phone number (any relevant detail the pt provided.)"]
 
 
• Send High-priority Page to on-call Study Physician.
 
 
CRC Note: You do NOT need participant's consent to call 911 if you feel there is a possibility of immediate risk of harm to self or others.
	
If NO active plan or DECLINE TO STATE, explain to participant:
 
I am not a clinician; however, our study has clinicians who speak with any participant who tells us they've been feeling this way recently. I will have a study doctor call you within the next 3-4 days. I would also like to give you 2 national helpline and 1 text line numbers that you may find helpful. All numbers are available 24 hours/7 days a week. We will work together to get you feeling better.
 
National Hopeline Network: [name] or 1-([contact]
 
National Suicide Prevention Lifeline: [name] or 1-([contact] Crisis Text line: text START to [name]

[If PHQ9 completed by Participant online ]	

[The following pop-up message appears if a participant responds “1” (“several days”), “2” (“more than half the days”), or “3” (“nearly every day”) to the 9th question, regardless of active
	

action plan or not.]

Please note: We do not monitor this screener in real time, if this is an emergency call 911.

For more immediate attention, because you have been bothered by thoughts that you would be better off dead or of hurting yourself in some way in the last 2 weeks, you should call your physician or other healthcare professional right away or go to the emergency room.

You may also call the National Suicide Hotline at [name] / [contact] or the National Suicide Prevention Lifeline at [name] / [contact]. You may also text START to Crisis Text line number [name]. All these numbers are available 24 hours every day.

We will have a study doctor contact you within 3-4 days. In the meantime, do not delay seeking medical attention.

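### For PHQ9s completed online, the self-harm protocol drops the phone branch's risk tiers and sets no clinician-contact limit shorter than 3-4 days for an active suicide plan

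*Combined protocol and SAP*

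**What the plan says.** The self-harm text in Section 7.0 has a narrative and a table.

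The narrative says that if a patient is found to be suicidal during screening or follow-up, the protocol is there to "immediately alert the study supervising psychiatrist". After an item 9 score of 1, 2 or 3, the study asks whether the person has a suicide plan "and then follow the protocol based on the assessed level of risk". For PHQ9s completed at the start of Lumen sessions, the participant "will be offered the option to call an emergency contact", a national hotline or 911. The supervising psychiatrist and the intervention manager "receive immediate notifications, as outlined in the table below". The one time limit in the narrative then follows: "The study psychiatrist calls the participant within 3-4 days to conduct an assessment".

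The table has two halves. In the phone half, an active plan means that staff obtain the location, keep the participant on the line, ring 911 from a second phone and page the on-call study physician at high priority. No plan, or declining to say, means a doctor's call within 3-4 days and helpline numbers. In the online half, a single pop-up follows a score of 1-3 "to the 9th question, regardless of active" plan status. It says "We do not monitor this screener in real time, if this is an emergency call 911", directs the participant to a physician, the emergency room and crisis lines, and closes with "We will have a study doctor contact you within 3-4 days".

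**The concern.** The phone half treats an active plan as an emergency on which staff act during the call. The online half and the session-PHQ9 narrative attach one contact limit to every positive item 9. As written, a participant who reports a plan online has the same limit that the phone half gives to someone with no plan.

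The online route matters because Section 7.0 itself names the PHQ9 before each PST session as a point where suicidality may emerge after enrollment. Appendix 1 (Sections A and B) has those forms completed before each session through links texted to the participant's own phone, with no staff member on the line. Section 5.0 also lets patients self-screen online. The emergency resources shown there are useful, but each depends on the person at risk choosing to use them. The possible harm is irreversible.

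**Working it through.** No statistical formula applies. The check sets the branches of Section 7.0 side by side and then looks for a shorter limit elsewhere.

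**1. The branches compared**

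| Route and plan status | Staff action stated | Limit for clinician contact |
|---|---|---|
| Phone, active plan | 911 during the call; high-priority page to on-call physician | Immediate escalation |
| Phone, no plan or declined | Helpline numbers given | 3-4 days |
| Online, active plan | Immediate alert (narrative); no separate step in the table | 3-4 days |
| Online, no plan | Immediate alert (narrative); no separate step in the table | 3-4 days |

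The third row carries the limit of the second row, not of the first.

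**2. Size of the limit.** 3 x 24 = 72 hours and 4 x 24 = 96 hours. This is an outer bound: an earlier call is allowed but not required.

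**3. Search for a shorter limit.** The rest of Section 7.0, Section 11.0 and Appendices 1 and 2 give none for a plan reported online.

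**4. The alert.** The narrative promises immediate notification and refers to the table for its outline. The online half of the table outlines no notification and tells the participant that the form is not watched in real time. The two can coexist, since an automatic alert does not need live monitoring, but the table does not say when the alert fires or how urgent it is.

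**5. Is the plan question on the online form?** The narrative says that it is asked, and the active-plan exclusion in Section 4.2 needs the answer. No section names the form that collects it. Both readings leave a gap:
- If it is asked, no stated limit becomes shorter when the answer is yes.
- If it is not asked, plan status may stay unknown until the 3-4 day call.

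**The case against.** The strongest defense is that the pop-up is text for participants, not a staff procedure. Its reference to plan status controls when the message appears; it does not tell staff to treat all cases alike. Staff who follow the whole narrative have an immediate alert and an instruction to respond to the level of risk, and referral depends on urgency. Participants are sent to 911, the emergency room and hotlines at once. A web form cannot keep someone on the line, and an active plan at screening is an exclusion.

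Most of this stands, and it rules out some stronger readings:

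- A reader might infer that nobody is told for 3-4 days, or that staff must wait. The documents do not support this: the alert is immediate and the limit is an upper one.
- A reader might infer that the online form omits the plan question. The text does not settle it.
- A reader might multiply participants by sessions to measure the exposure. That product is not a maximum: Appendix 1 has surveys redone when they are more than 3 days old at the session, Section 7.0 lets waitlist participants take Lumen after week 16, and online self-screens add more forms. It would also count all PHQ9s, not those reporting a plan.
- A reader might infer from the footnotes to Appendix 2 that session forms are the sole PHQ9s after screening. The schedule itself appears to mark a PHQ9 at week 0, so this is not secure.

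What the defense does not supply is a time. The instruction to follow the assessed risk has tiers to follow only in the phone half. For session forms the narrative repeats 3-4 days without regard to plan status. A first call on day 4 to someone who has reported a plan would comply with the protocol.

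**Conclusion.** The point holds as a gap in response time, not as an absence of response. For online PHQ9s the protocol does not carry over the phone branch's tiers, and the only stated limit for clinician contact is 3-4 days (72-96 hours) whatever the plan status.

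This rests on two readings: that the online half of the table covers session forms as well as self-screening, as its general heading suggests, and that no operating procedure outside these documents sets a shorter limit. If the pop-up applied to screening alone, the narrative would still give 3-4 days for session forms.

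The documents give no rate of item 9 or plan endorsement, so the number of participants affected cannot be estimated and the event should not be described as either common or rare. Sample size, power, alpha and outcome analyses are unaffected. The point is best classed as a cheap improvement to patient safety.

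**What to change.** Amend the online half of the Section 7.0 table and the matching narrative sentence:

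- Show the plan question on every online PHQ9 after an item 9 score of 1-3.
- If a plan is endorsed, send the notification already promised as high priority to the on-call study physician named in the phone half, require a clinician call the same day, and show a pop-up worded for that case.
- Keep the 3-4 day call only for no plan or decline to state.
- State in the online half that the notification fires when the form is submitted.

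The cost is a REDCap branching rule and priority flag on an existing form and alert, a second pop-up text and an IRB amendment. No visits or outcome data are added.

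The real burden is same-day clinician cover, weekends included. The phone half already assumes an on-call physician, but no roster is described, and the Summary of Edits (V7) records that the internist who backed up the psychiatrist was removed because enrollment is small. The amendment should therefore say who covers when the psychiatrist is unavailable.

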**Protection against injury, discomfort, and distress with brain imaging. (Pilot RCT only)**

MRI is non-invasive, widely used, and safe. Routine contraindications to MRI include presence of any metal implants (pacemaker, aneurysm clips, neurostimulators, cochlear, eye implants, old or very fresh tattoos). Participants are thoroughly assessed for MRI eligibility during screening using the well-established procedures as in the ENGAGE-2 study (protocol #2018-1174). A small number of people may feel claustrophobic inside the MRI machine. The study can be immediately stopped via button press if this occurs. Sometimes subjects report a temporary, slight dizziness or light-headedness when they come out of the scanner. Study personnel and technicians are on site during all acquisitions to address any such discomfort. To minimize fatigue, sufficient breaks are provided to participants during the scanning procedure, and the study coordinator conducting the scan regularly inquires as to whether there is anything that s/he can do to facilitate the participant's comfort. In the event of adverse effects related to MRI scanning, study personnel and medical staff are on-site for consultation and assistance. The UI Hospital Emergency Room is less than a 5-minute drive from the scanning center. If there are any adverse events at any time during the MRI procedure, the study coordinator terminates the scanning session, provides a debriefing, and contacts study psychiatrist ([name]) for assistance and follow-up for the participant.

According to the National Institute of Mental Health (NIMH) Council Workgroup on MRI Research and Practices (September, 2005), "there is no known risk of MR brain scanning of a pregnant woman to the developing fetus for scanning at 4T or less, and no known mechanism of potential risks under normal operating procedures." Notwithstanding, subjects are warned about potential risks not yet discovered in the informed consent form. Before each scan, female participants are asked if they are or are trying to become pregnant and when they had their last menstrual period. Any woman who indicates that she is pregnant will not be scanned. Any woman who indicates that she is trying to become pregnant or who is experiencing a late menstrual period is asked to complete a urine pregnancy test, which if positive will preclude the subject from being scanned.

If study personnel observe any unusual features in the MRI scan at the time of acquisition or an incidental finding, or abnormality on MRI scans, staff requests a clinical neuroradiological report on the scan from the neuroradiologists at the Center for MR Research who are on call to provide these reports as required, as part of the infrastructure of the Center's facility. During the consenting process, all participants are informed about the potential risks of discovering an incidental finding or abnormality on their MRI scan. If an abnormality is found in a participant's MRI scan, PI [name] contacts the participant and refers him/her for medical follow-up for the problem if the participant requests, including a referral to a PCP. If

a participant has a PCP, the PI contacts the PCP, at the request of, and with verbal permission from the participant, to inform him/her of the finding on the MRI scan and to help him/her get the participant appropriate follow-up. The decision as to whether to proceed with further examination and/or treatment lies solely with the participant and his/her PCP.

**Protection against breaches of participant privacy and confidentiality.** All investigators and their staff are adequately trained to protect participant privacy and sign an agreement to do so. All information obtained from research participants during the study are considered strictly confidential and are only used and disclosed as permitted under the HIPAA regulations. All eligible participants must sign a HIPAA authorization as part of the informed consent form in order to participate. They also have the option to agree to sharing of their de-identified data through the NIMH Data Archive (NDA). Only aggregate data will be included in scientific presentations and publications resulting from this study.

To ensure data security, security protocols are incorporated at multiple levels. First, participants are assigned unique anonymous IDs (“Study Participant ID”) that are used as a proxy for mapping all PHI and PII (personally identifiable information). A mapping document that links Study Participant IDs to the corresponding PHI and PII is maintained separately from all study-related data of participants and stored in a secure manner (e.g., encrypted REDCap database on a secure server behind the university’s fire wall). Only a designated subset of study personnel who have a need to know (e.g., PIs and recruitment personnel) have access to the mapping document.

#### Aim 1: Formative Research

**Formative user study sessions:** present minimal risk to research participants and prudent measures are taken to protect their privacy and confidentiality. Participants are informed in advance about the discussion topics so that they may make an informed decision to participate. For the formative user study sessions, participants are made aware of study team observers present during the sessions. Study personnel alerts participants before beginning audio-recording of sessions. Transcriptions of audio-recordings do not identify participants, instead individuals are referred to as “Respondent #.” If names or locations of attendees are recorded during a session, that information will not be included in the transcripts. Federal regulations require research records be retained for at least 3 years after completion of the research.

#### Aim 2: Pilot RCT

In addition to the protection measures described above, randomized participants who begin intervention per group assignment, receive study a iPad which utilizes the in-built encryption and 6-digit passcode protection and is configured with their first name, (as per informed consent.) Only first name will be used by Coach Lumen during intervention to facilitate participant engagement for treatment alliance. Additionally, the study iPads are in a “lock down” mode where participants cannot use them for any purposes but for tasks associated with the study.

No study data resides locally on the iPad. In order to maintain anonymity of the intervention participants, no personal identifiers (other than first name) are used during Lumen PST session data acquisition or storage. All Lumen PST session recordings and transcripts acquired by the Amazon Alexa application using the study iPad are stored on the AWS cloud within study configured accounts. The study-established AWS accounts are assigned coded “AWS IDs” (which are paired with “Study Participant ID”) are accessible only by study staff with a need to know. In case of a potential loss or theft of the study iPad, participants are instructed to immediately notify study staff and the AWS ID account access will be disabled.

The SPEAC study is a registered HIPAA account under a standardized Business Associate Addendum (BAA) held by UIC/UI Health with (AWS) which enables the covered entities to be HIPAA compliant.

Finally, participants are able to keep their study iPad for personal use after their AWS ID account access is disabled. Participants will be provided with instructions to remove the Lumen skill and to unlock the iPad to have a fully enabled device to keep. Alternatively, participants may choose to redeem the iPad for \$100. Participants in the waitlist control arm in the pilot RCT may choose to attend a Lumen Orientation visit to receive training and a Lumen PST-enabled iPad after the end-of-study assessments at 16 weeks post randomization. These options are explained to study participants during the informed consent and reiterated to waitlist control participants who choose to receive Lumen PST after the end of the study.

**Protection against accidental recording.** Accidental recording is a commonly raised concern regarding voice-enabled technologies. In the case of Lumen, the application is installed on the locked-down and encrypted study iPad. In order to prevent accidental recording, the following protections are implemented: First, the iPad has a keypad lock. Recording takes place only in the unlocked mode, after the participant opens the Alexa app, and gives permission verbally (using specific “wake phrases” such as “Launch Lumen Session,” or by tapping the option on the iPad screen. Second, participants are informed that all Lumen sessions are recorded and give explicit permission for this as part of their informed consent process. Third, if the study iPad is left unattended during an active session, the iPad locks after 10-seconds, and after 30 seconds of no verbal input from the participant, the Lumen session shuts down (preventing any further recording). Once the participant returns, they must go through the process of unlocking iPad and waking Lumen to actively resuming their session.

**Potential benefits to participants.** Eligible participants in the study have mild or moderate depressive and/or anxiety symptoms that are not treated. They receive PST by interacting with Lumen on a secure study iPad. Waitlist controls have the option to receive Lumen after their 16-week assessments. PST is a brief skill-enhancing psychotherapy with robust evidence for efficacy in treating depression and anxiety. PST focuses on improving one’s skills involved in solving personal real-life problems and is easy for most people to understand. Its stepwise, patient-driven approach is also easy to follow. Lumen is a voice-enabled, PST-trained agent who will undergo iterative design development and refinement based on information gathered from evaluation cycles and rigorous testing. Through interacting with Lumen, participants in the study may benefit from having PST at their fingertips and experience improvements in psychological symptoms, functioning and quality of life. If shown successful in this developmental R61 phase of the project, Lumen will undergo further confirmatory testing (in the R33 phase) and may downstream carry the potential to be scaled for use by people with depression and/or anxiety who cannot or will not seek professional help or who desire as-needed, personal help beyond what conventional treatment models can offer.

